2.2 Analysis sets

Analysis sets used for the final CSR are described below. Further analysis sets as defined in the protocol and reported in the core CSR will not be repeated.

2.2.1 Full Analysis Set

The Full Analysis Set (FAS) comprises all randomized patients who have received at least one dose of study drug (osilodrostat or placebo). According to the intent-to-treat (ITT) principle, patients will be analyzed according to the treatment and stratum they have been assigned to during the randomization. This is the default analysis set for efficacy. The randomization is stratified by history of pituitary irradiation yes/no.

2.2.2 Safety Set

The Safety Set (SS) includes all patients who received at least one dose of study drug (osilodrostat or placebo). Patients will be analyzed according to the study drug received, where treatment received is defined as the randomized/assigned treatment if the patient took at least one dose of that treatment or the first treatment received if the randomized/assigned treatment was never received.

2.2.3 Withdrawal of informed consent

Any data collected in the clinical database after a subject withdraws informed consent from all further participation in the trial, will not be included in the analysis datasets. The date on which a patient withdraws full consent will be recorded in the eCRF.

Third party data e.g. PK, biomarker etc. collected in the clinical database without having obtained consent for collection will not be included in the analysis datasets. These data will be excluded by the presence of the appropriate protocol deviation criterion.

2.3 Patient disposition, demographics and other baseline characteristics

2.3.1 Demographics and baseline characteristics

All demographic and baseline disease characteristics were summarized in the interim CSR. They will not be reported in the final CSR.

2.3.2 Patient disposition

Patient disposition will be tabulated for FAS. The summary will include the number of patients who were randomized, treated, permanently discontinued from study treatment.

The following summaries will be presented: % is based on total number of FAS patients:

- Number (%) of patients who were randomized (based on data from IRT system)
- Number (%) of patients who were randomized but not treated (based on eCRF DAR page not completed for any study treatment component)
 - Primary reason for not being treated (based on eCRF End of Treatment Phase Completion page)
- Number (%) of patients who were treated (based on eCRF DAR page of each study treatment completed with non-zero dose administered)
 - Number (%) of patients who discontinued the study treatment phase (based on eCRF End of Treatment Phase page)
 - Primary reason for study treatment phase discontinuation (based on eCRF End of Treatment Phase Completion page)
 - Number (%) of patients who discontinued in Period 1 (prior to Week 12)
 - Primary reason for discontinuation in Period 1
 - Number (%) of patients who discontinued in Period 2 (Weeks 13 to 48)
 - Primary reason for discontinuation in Period 2
- Number (%) of patients who completed core phase (week 48)
 - Completed Week 48 and did not enter Extension phase
 - Completed Week 48 and entered Extension phase
 - Number (%) of patients who discontinued in the Extension
 - Primary reason for discontinuation in the Extension
 - Discontinued at or prior to Week 72 but after Week 48
 - Discontinued prior to Week 96 but after Week 72
 - Discontinued after Week 96
 - Number (%) of patients who completed extension

* Patients who completed Week 48 and did not enter extension phase are not counted as discontinuations.

2.3.3 Medical history

Relevant medical history and ongoing medical conditions were summarized in the interim CSR. They will not be reported in the final CSR.

2.3.4 Protocol deviations

The number (%) of patients in FAS with any PDs will be tabulated by deviation category (as specified in the study specification document (SSD)) by treatment group. All PDs will be listed. In addition, the number (%) of patients in the FAS with any COVID-19 related protocol deviation will be tabulated by deviation category (as specified in the Study Specification Document) overall and by treatment group.

2.3.5 COVID-19 impact

As per Novartis guidance, the start date, in a given country or region, is being defined as the approximate time point at which, according to the WHO situation reports and the Johns Hopkins database, the number of confirmed COVID-19 infections started to increase significantly (around 100 confirmed cases) and/or governments started to take measures (such as stay-at-home orders) to contain the epidemic, whichever occurred first (China: January 1, 2020; Other countries with study sites: March 1, 2020).

The pandemic impact will be assessed based on two subsets:

- Before pandemic set: Patients who completed (or discontinued) the trial before the pandemic start date in their region/country
- During pandemic set: Patients with at least one on-treatment assessment or treatment-emergent event during the pandemic dates as defined for their region/country

A summary of the number of patients in the pandemic sets within each country will be provided. The number of patients who completed or discontinued during the core phase, Week 48-72 and after Week 72 will be tabulated by pandemic set.

2.4 Treatments (study treatment, rescue medication, concomitant therapies, compliance)

2.4.1 Study treatment / compliance

The exposure for study period 1 (week 1-12) and 2 (week 13-48) was summarized in the interim CSR. In the final CSR the exposure to the study drug (osilodrostat) will be summarized for the overall study period including the extension period after week 48.

2.4.1.1 Duration of exposure

Duration of exposure (weeks) = (min (date of last date of study treatment, date of data cut-off, date of death) – date of first date of study treatment + 1)/7

In the overall period, the total duration of exposure to osilodrostat is considered by taking account of the duration of exposure in both Period 1, Period 2, as well as extension. For patients in the placebo arm, exposure to placebo is excluded. The duration calculation includes the periods of temporary interruptions.

Summary of duration of exposure to study treatment will include categorical summaries and continuous summaries using appropriate unit of time.

2.4.1.2 Dose reduction/interruption

The number of patients who have at least one dose reduction or interruption, and the corresponding reasons will be summarized for the overall study period. Although patients may have multiple dose reductions or interruptions with the same reason, patients will be counted only once for each distinct reason.

The total daily dose administered and reason for dose change will be listed with UFC information by date.

2.4.2 Prior, concomitant and post therapies

Concomitant therapy is defined as all interventions (therapeutic treatments and procedures) other than the study treatment administered to a patient coinciding with the study treatment period. Concomitant therapy include medications (other than study drugs) starting on or after the start date of study treatment or medications starting prior to the start date of study treatment and continuing after the start date of study treatment.

Concomitant medications will be coded using the World Health Organization (WHO) Drug Reference Listing (DRL) dictionary that employs the WHO Anatomical Therapeutic Chemical (ATC) classification system and summarized by lowest ATC class and preferred term using frequency counts and percentages. Surgical and medical procedures will be coded using MedDRA and summarized by SOC and preferred term.

All concomitant therapies will be listed. Any concomitant therapies starting and ending prior to the start of study treatment or starting more than 30 days after the last date of study treatment or safety follow-up whichever is later will be flagged in the listing. The safety set will be used for all concomitant medication tables and listings.

Concomitant medications and significant non-drug therapies will be summarized using frequency counts and percentages by ATC class, preferred term and treatment group within the overall study period.

2.5 Analysis of the primary objective

The primary objective is to demonstrate the superiority of osilodrostat compared to placebo in achieving a complete response ($mUFC \leq ULN$) at week 12. The results were reported in the interim CSR, and will not be performed for the final analysis.

2.6 Analysis of the key secondary objective

The key secondary objective is to assess the complete response rate (proportion of enrolled patients with $mUFC \leq ULN$) in both arms combined at Week 36 in patients receiving

osilodrostat treatment. The results were reported in the interim CSR, and will not be repeated for the final CSR.

2.7 Analysis of secondary efficacy objectives

2.7.1 Assess the overall response rate

Proportion of complete responders (enrolled patients with $mUFC \leq ULN$), partial responders (enrolled patients with $mUFC > ULN$ and at least 50% reduction from baseline), and overall responders (enrolled patients with $mUFC \leq ULN$ or have at least 50% reduction in $mUFC$ from baseline and $> ULN$) will be summarized using point estimates for all scheduled visits in the core and extension phase at which UFC is collected (provided [adequate follow-up](#), as defined in section 2.1.1, [Criteria of adequate follow-up for time points in the extension phase](#)).

Due to the COVID-19 (Coronavirus) pandemic, planned visits may have been cancelled, potentially resulting in missing UFC evaluations. Patients with insufficient information due to any reason at a visit will be considered as non-responder for that visit. The number of patients with non-response due to missing visits linked to the pandemic (recorded as COVID-19 related PD) will be summarized.

To explore the impact of the COVID19 pandemic in the extension phase, individual patient's doses and overall response status over time will be graphically displayed together with pandemic start date.

The FAS will be used for this analysis.

2.7.2 Assess the change in mUFC during the Core and Extension periods of the study

For the actual value and change in $mUFC$ from baseline, descriptive summaries will be provided for every scheduled visit in the core and extension (provided [adequate follow-up](#), as defined in section 2.1.1, [Criteria of adequate follow-up for time points in the extension phase](#)) at which UFC is collected. The FAS will be used for the analysis.

2.7.3 Compare the time-to-first control of mUFC during the placebo-controlled period between patients randomized to osilodrostat and placebo

The results were reported in the interim CSR, and will not be repeated for the final CSR.

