Escape	Defined as loss of control of mUFC after week 26 (mean UFC $>$ 1.3 x ULN on two consecutive visits on the highest tolerated dose of osilodrostat and not related to a dose interruption or dose reduction due to safety reasons) after prior mUFC normalization
Optional extension phase	Week 48 through Week 96
Study drug	Osilodrostat or placebo
Medication number	A unique identifier on the label of each blinded study drug package linked to one of the treatment groups of a study
mUFC	mUFC at a particular visit is the arithmetic mean of the urinary free cortisol (UFC) levels calculated from three 24-hour urine samples collected at screening, baseline, Week 12, Week 36, Week 48 and Week 12 follow up. The arithmetic mean of UFC from two 24-hour urine samples will be evaluated at all other study visits
Overall Response	Defined as either complete response (mUFC \leq ULN) or partial response (mUFC $>$ ULN with \geq 50% reduction from baseline) during study treatment
Partial Response	Defined as mUFC $>$ ULN with \geq 50% reduction from baseline during study treatment
Period	Period 1: Day 1 through Week 12. Period 2: Starts immediately after the Week 12 visit through Week 48.
Randomization number	A unique treatment identification code assigned to each randomized patient, corresponding to a specific treatment arm assignment
Subject Number (Subject No.)	A unique identifying number assigned to each patient/subject/healthy volunteer who enrolls in the study
Study drug discontinuation	Point/time when patient permanently stops taking study drug for any reason
Variable	Identifier used in the data analysis; derived directly or indirectly from data collected using specified assessments at specified time-points
Withdrawal of Consent	Withdrawal of consent occurs only when a patient does not want to participate in the study any longer, and does not want any further visits or assessments, and does not want any further study related contact

Amendment 2 (20-Dec-2019)

Amendment rationale

As of 10 December 2019, the study is fully enrolled and 45 patients are still on treatment. Of the 45 patients on treatment, 10 are active in the core phase of the study and 35 are active in the optional extension phase of the study. The last patient enrolled in the study should complete the 48 week core period by the end of Feb-2020.

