2.1.1 General definitions

Study drug

Throughout the SAP, investigational drug refers to osilodrostat, and study treatment/ study drug refers to osilodrostat or placebo.

Overall study period

The overall study period refers to the complete study duration (including core and extension period) with data presented by the osilodrostat arm, placebo arm excluding placebo-control period, and overall patients (excluding data of placebo arm collected during placebo-control period).

Date of study treatment

The start date of study treatment is defined as the first date when a nonzero dose of study treatment was administered and recorded on DAR eCRF. The date of first administration of study treatment in period 1 will be referred as the start date of study treatment.

The last date of study treatment is defined as the last date when a nonzero dose of study drug was administered and recorded on DAR eCRF.

Study day

Study day is used to represent an evaluation, a measurement or an event (e.g. AE onset, laboratory abnormality occurrence, disease progression, etc.). The study day is calculated as

Study day = date of assessment – start date of study treatment + 1 (if date of assessment is after start date of study treatment)

Study day = date of assessment – start date of study treatment (if date of assessment is before start date of study treatment)

For any assessment or events such as baseline characteristics or medical history that is supposed to occur prior to start date of the study treatment, study day will be negative. There is no Day 0 defined.

Study day associated with a UFC assessment

The study day associated with a UFC assessment at any particular visit is defined as the study day of the last UFC sample collection for that visit.

Calculating mean UFC

It is scheduled to collect three individual 24 hours Urine Free Cortisol (UFC) samples at visits Week 1, 12, 36, and 48, and two UFC samples at all other visits. For a given visit, Mean Urine Free Cortisol (mUFC) is the mean of all available (with a minimum of 2) individual UFC values determined at a central laboratory. In the case that only one or no UFC value is available, the mUFC will be considered missing for that visit.

Calculation of proportions of responders

All randomized patients will be included in the analysis for calculating the proportion of responders at time points up to Week 48 based on the FAS.

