For calculation of proportion of responders beyond Week 48 (e.g. a time point in extension phase), the following rules will be applied to determine whether patients are included in the analysis.

- 1) patients who declined to enter optional extension phase after completion of the core phase will be excluded.
- 2) patients who completed the extension phase will be included until their individual end of study dates (EOT EXT visit, as per Protocol Amendment 02)
- 3) patients who discontinued prior to the data cutoff date for the Final DBL will be included for visits they could have completed if they had continued until week 96 or data cut off for the analysis (whatever occurs earlier), but excluded for further visits. For example, if the last completed scheduled visit for an early discontinued patient is Week 84, and the time between data cutoff and last completed scheduled visit is 20 weeks, he/she will be included in the analyses up to Week 96.

If included in the analysis for calculating the proportion of responders at a given timepoint, patients who discontinued before this timepoint will be counted as non-responders.

Criteria of adequate follow-up for time points in the extension phase

For a given time point in the extension phase, it will be considered to have adequate follow-up to be included in the reporting activities if there are at least 15 patients available for the analysis at that time point.

Time unit

A year length is defined as 365.25 days. A month length is 30.4375 days (365.25/12). If duration is reported in months, duration in days will be divided by 30.4375. If duration is reported in years, duration in days will be divided by 365.25.

Baseline

Baseline values for efficacy and safety evaluations are defined as the last assessment available before or on the start date of study treatment. If patients have no assessments as defined above, the baseline result will be missing.

Follow up

Regular safety follow-up is scheduled at 30 days after the last date of study treatment. In addition, for patients who discontinued study treatment during Period 1 (Weeks 1 to 12), reasonable efforts should be made to follow the patients and perform the assessments as indicated in protocol visit evaluation schedule table (protocol Table 7-1a) up to and including Week 12.

Visit number and time window

The following visit schedule tables are generated from TDM/TV domain.

Table 2-1 Scheduled visits in core phase

Core study Visit	Day/Week	Clarifying Notes

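### Final SAP 2.7.1 counts pandemic-missed mUFC as non-response and plans no response rate that sets those visits aside

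*SAP*

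**What the plan says.** There are two SAPs: the core SAP (1 April 2019, Week 48 report) and the final SAP (1 December 2020, dated before the final database lock). The point concerns the final SAP.

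- **Missing-data rule.** Final SAP 2.7.1 gives complete, partial and overall response as point estimates at each scheduled UFC visit. It notes that the pandemic may have led to cancelled visits, then states: "Patients with insufficient information due to any reason at a visit will be considered as non-responder for that visit". Under 2.1.1, "In the case that only one or no UFC value is available, the mUFC will be considered missing for that visit".
- **Pandemic outputs on response.** Section 2.7.1 adds: "The number of patients with non-response due to missing visits linked to the pandemic (recorded as COVID-19 related PD) will be summarized". It does not say that this is done visit by visit. For each patient, doses and "overall response status over time will be graphically displayed together with pandemic start date".
- **Other pandemic outputs.** Sections 2.3.4 and 2.3.5 tabulate COVID-19-related deviations, patients per pandemic set by country, and disposition by pandemic set. No response rate by pandemic set is planned.
- **Denominators.** Under 2.1.1 an extension visit is reported "if there are at least 15 patients available for the analysis at that time point". Patients who complete the extension leave the denominator at their own end of study. Discontinued patients stay in as non-responders for visits they could still have reached.
- **Core SAP.** It uses the same rule at Week 12 (2.5.3) and Week 36 (2.6.3). It pairs the rule with multiple imputation as a sensitivity analysis in 2.5.4, and says in 2.6.3 that this will be considered. The final SAP has no counterpart.

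**The concern.** The final report is about long-term efficacy. The Week 12 and Week 36 analyses are not repeated in it (final SAP 2.5 and 2.6), so response over time is one of its main efficacy outputs. Under 2.7.1 three different things enter that output as the same value: mUFC observed to be out of control, discontinuation, and a visit that did not take place because of the pandemic. The third says nothing about the drug. If it occurred, a reader comparing Week 48 with later weeks could take the resulting drop for loss of response.

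The planned count and plot do not settle this. Without counts by visit, a rate that leaves the missed visits out cannot be recalculated. The plot shows response status, which may already have been coded by the rule. Neither gives an alternative rate or an interval.

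**Working it through.** **Is there a figure in the plan to reproduce?** No. The documents give no expected extension response rate, no denominators by visit and no number of pandemic-missed visits. The stated power figures concern Weeks 12 and 36 and do not bear on this point.

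**Which visits can be affected?**

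- Protocol Table 7-2 schedules extension UFC at Weeks 60, 72, 84 and 96, at Week 108 and every 24 weeks afterwards for anyone still on study, at end of treatment and at follow-up.
- The pandemic start date is 1 January 2020 in China; final SAP 2.3.5 continues: "Other countries with study sites: March 1, 2020".
- The Amendment 2 rationale reports 45 patients on treatment on 10 December 2019, 10 in the core phase and 35 in the extension. It adds: "The last patient enrolled in the study should complete the 48 week core period by the end of Feb-2020". On that schedule, core visits could be affected only in China, in January and February 2020.
- A patient already in the extension on 10 December 2019 was due at Week 60 at most 12 weeks later: 10 December 2019 + 84 days = 3 March 2020. Outside China, exposure at Week 60 is therefore largely confined to the 10 patients then still in the core phase.
- The 18 patients treated by 20 November 2017 (Amendment 1 rationale) were due at Week 96 by late September 2019, before the pandemic.
- Amendment 2 was to be approved locally after the last patient completed the core phase, with end-of-treatment visits within 4 weeks of approval. On that schedule the close-out visits fall at about or after 1 March 2020. Local approval dates are not given.

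**Size of the effect.** Let n be the denominator at a visit, m the number of patients in it whose mUFC is missing because of the pandemic, and p the true response rate. Assume that being missed is unrelated to response.

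- Expected observed responders = p × (n − m)
- Rate under the rule = p × (n − m)/n, so the drop is p × m/n
- Rate with missed visits set aside = p × (n − m)/(n − m) = p

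Inputs: p = 60% is the sponsor's planning value for Week 36 (final SAP section 3), and p = 80% is an assumption added to show a range. n = 15 is the smallest reportable extension visit. n = 35 is the extension head-count of December 2019, used only for scale. m is assumed.

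Per missed visit at p = 60%: 0.60/35 = 1.7 points; 0.60/15 = 4.0 points. At p = 80%: 2.3 and 5.3 points.

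| n | p | m = 0 | m = 1 | m = 3 | m = 5 |
|---|---|---|---|---|---|
| 35 | 60% | 60.0% | 58.3% | 54.9% | 51.4% |
| 35 | 80% | 80.0% | 77.7% | 73.1% | 68.6% |
| 15 | 60% | 60.0% | 56.0% | 48.0% | 40.0% |
| 15 | 80% | 80.0% | 74.7% | 64.0% | 53.3% |

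The ceiling per missed visit is 1/n (2.9 points at n = 35, 6.7 at n = 15), reached only if the missed patient would certainly have responded.

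**The case against.** The rule is prespecified, conservative and the same as in the core SAP. It is applied to descriptive estimates in an uncontrolled open-label extension; the protocol's own response endpoints are Weeks 12, 36 and 48. All of that stands, and it is why the rule should remain the main summary. Consistency with the core SAP is only partial, though, because the accompanying sensitivity analysis was not carried over.

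The pandemic is also not ignored. Pandemic-linked non-responses are counted, patients are plotted against the pandemic start date, and deviations and disposition are tabulated. A reader might infer from the rule alone that the plan does nothing about these visits; sections 2.3.4, 2.3.5 and 2.7.1 show otherwise. What is missing is narrower: counts by visit, and a response rate without the missed visits.

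Nor does the long-term picture rest on this rule alone. For mUFC and its change, section 2.7.2 says "descriptive summaries will be provided for every scheduled visit in the core and extension", subject to adequate follow-up and with no imputation stated. Time-to-escape (2.7.4) needs two consecutive mUFC values above 1.3 × ULN, so a missed visit is not an escape. This stands, but neither output is a response rate.

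Finally, exposure is limited. UFC visits in the extension are sparse, some patients passed Week 96 before the pandemic, and completers leave the denominator. This also stands and argues against a large effect. The 4-week exit rule does not remove the exposure, because it was to start only once the core phase had ended.

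**Conclusion.** The gap is real and modest. Pandemic-missed mUFC counts as non-response, and no response rate in the final SAP sets it aside. If m such visits were missed, the descriptive rate at that visit would be lowered by an expected p × m/n: about 1.7 points each at n = 35 and 4.0 points each at n = 15, for p = 60%. This rests on missed visits being unrelated to response and on illustrative values of n.

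Three stronger readings are tempting and not supported:

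- That the long-term response trend is in fact biased downward. The SAP says only that visits may have been cancelled; m is not given and may be zero, in which case nothing changes.
- That every missed visit costs 1/n. That is the ceiling, not the expected loss.
- That 35 is the denominator of some visit. It counts patients at different study weeks on one date, whereas the denominators in 2.1.1 also hold earlier completers and discontinued patients.

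No hypothesis test is affected. The primary and key secondary results were reported from the core analysis, and the mUFC summaries and time-to-escape do not use this coding.

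**What to change.** Keep missing = non-responder as the main summary and add two items to final SAP 2.7.1:

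1. Give the number of pandemic-linked missing mUFC values by visit.
2. For each affected visit, core or extension, add a supportive response rate with 95% CI beside the main rate. Remove from numerator and denominator those patients still on treatment whose mUFC is missing with a COVID-19-related protocol deviation. Discontinued patients and patients missing for other reasons remain non-responders. The Clopper-Pearson interval of Protocol 10.5.2.1 can be used.

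The cost is one extra table, built from a deviation flag that 2.3.4 and 2.7.1 already require. It can be specified before the final database lock. The drawback is that the supportive rate assumes pandemic-missed visits are unrelated to response, which the table should state. If no visits were missed, the two rates coincide.
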